8.7.3 Stopping rules for interim toxicity and relapse futility

- Study data will be analyzed for relapse rates within 3 months for efficacy assessment. Such early futility assessment will be done when the first 14 patients have completed the 3-month follow-up in the study. If there are 9 or more relapses out of 14 patients during the futility assessment, enrollment will be stopped due to futility. Otherwise an additional 54 patients will be accrued for a total of 67 patients in the study. By the end of the study, if there are 32 or more relapses observed, further investigation will not proceed. In this study the rate of relapse in pediatric acute leukemia post-transplant is assumed to be 40% (as shown in our pilot study), azacitidine +/- DLI would reduce the 2-year relapse rate by approximately 40% to a rate of 25% and that the toxicity rate in pediatric acute leukemia post-transplant under azacitidine +/- DLI would be 20%. The stopping rules for toxicity and relapse rate under sequential design of multiple endpoints are shown below:
- For patients receiving DLI, a subset analysis of incidence of Grade III-IV aGVHD and mortality secondary to GVHD will be performed when a new patient is diagnosed with Grade III-IV GVHD or chronic GVHD.
 - Reported rates of grade III-IV acute GVHD following DLI range from 20-35%; GVHD-related mortality ranges from 5-15%.
 - If rates of Grade III-IV aGVHD or GVHD-related mortality in this study exceed published rates, enrollment and further DLI administration will be suspended while further safety analysis is performed.

Patients on Study	<14	15-21	22-28	29-35	36-42	43-49	50-56	57-63
Number of patients with SAE (Toxicity)	>8	≥10	≥13	≥16	≥18	≥21	≥23	≥26
Number of patients with relapse in 3 months	>9	≥13	≥16	≥19	≥23	≥26	≥29	≥32

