1.2 Predictors of post-transplant relapse

Mixed chimerism (MC) is the presence of both host's and donor's hematopoietic cells after allogeneic transplant. With the introduction of quantitative and frequent measurements of chimerism, the relationship between the presence of host cells and the relapse of acute leukemias after allogeneic transplant was recognized. In 1998, Bader et al. showed that pediatric patients with increasing amount of host (autologous) cells on their chimerism testing following allogeneic transplant have significantly increased risk of relapse (5). In their study, 36/54 children had complete donor chimerism and 19% of them relapsed, 10/54 children had increasing amounts of host cells post-transplant (increasing host chimerism) and 90% of them relapsed; in contrast, 8/54 children had decreasing amount of host cells following transplant (decreasing host chimerism) and none of them relapsed (5). Similar results were obtained by Barrios et al. in adults; 93% of patients with increasing host chimerism and 27% of patients with full donor chimerism relapsed, respectively (6).

Patients with increasing host chimerism sustained relapses between days 36 and 450 of their follow-up. Increasing host chimerism preceded relapse by a median of 74 days (6). The investigators concluded that frequent and sensitive measurement of chimerism after transplant is a useful tool for identifying a group of patients with a very high risk of relapse in whom further immunotherapy would be justified. Additionally, Bader and colleagues studied the origin of cells found in patients with mixed chimerism. In the early post-transplant period, mixed chimerism was caused predominantly by normal recipient hematopoietic cells. This finding supports the hypothesis that a state of mixed hematopoietic chimerism may reduce the clinical GVL effect of alloreactive donor-derived effector cells in patients with acute leukemias, and thus facilitate the proliferation of residual malignant cells that may have survived the preparative regimen (7).

The presence of minimal residual disease (MRD), either immediately prior to HSCT, or following HSCT, has been correlated with decreased survival and increased risk of relapse in both ALL (8) AML (9) patients (10). An MRD-guided strategy of reduction of immunosuppression without DLI or azacitidine resulted in overall survival of 72% in patients with MRD <0.1%, and 40.4% in those with MRD>0.1% (11). This protocol plans to build on

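### The futility rule counts 3-month relapses against limits built around the 40% two-year rate, so it has almost no chance of stopping an ineffective regimen

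*Combined protocol and SAP*

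**What the plan says.** Section 8.7.3 sets the window: "Study data will be analyzed for relapse rates within 3 months for efficacy assessment". It sets the timing of the look: "Such early futility assessment will be done when the first 14 patients have completed the 3-month follow-up in the study". It sets the limit: "If there are 9 or more relapses out of 14 patients during the futility assessment, enrollment will be stopped due to futility". If the limit is not reached, "Otherwise an additional 54 patients will be accrued for a total of 67 patients in the study".

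The table in that section continues the rule in bands ending at 21, 28, 35, 42, 49, 56 and 63 patients, with limits of 13, 16, 19, 23, 26, 29 and 32. The row is labelled "Number of patients with relapse in 3 months". The text adds an end-of-study limit of 32 relapses.

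The rates behind the rule are a 40% relapse rate from the pilot study and the expectation that "azacitidine +/- DLI would reduce the 2-year relapse rate by approximately 40% to a rate of 25" per cent. The same pair sizes the trial in Section 8.4.1, and the synopsis judges success on relapse at two years. No 3-month reference rate appears anywhere. Section 8.7.2 prints early-stopping probabilities for the SAE limits. Section 8.7.3 prints none for relapse.

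**The concern.** A limit of 9 in 14 is an observed proportion of 64%. That is a sensible warning level if the count is compared with a 40% rate over the same period. Here the count covers three months and the 40% belongs with a two-year endpoint. Unless nearly all relapses come in the first three months, an ineffective regimen will produce far fewer than 9 early relapses in 14 patients.

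This is the plan's only numerical stop for lack of efficacy, and Section 7.1.2 relies on it. If it cannot trigger, a regimen that does nothing for relapse still enrols all 67 patients. Section 9.1 puts the risk of GVHD after withdrawal of immunosuppression and DLI at 50–65%, with roughly a 10% chance of dying from it. Passing the interim look would also be uninformative, although it could be read as encouraging.

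**Working it through.** **Inputs.** Limits and window: Section 8.7.3. Rates of 40% and 25%: Sections 8.4.1 and 8.7.3. The 3-month relapse rate under an ineffective regimen is not given. It is assumed here and varied from 5% to 40%.

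**Step 1: reproduce the printed limits.** Take a flat Beta(1,1) prior. After r relapses in n patients the posterior is Beta(1 + r, 1 + n − r). Find the smallest r with P(rate > 0.40) > 0.95 at the top of each band.

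| n | Printed limit | Smallest r | P(rate > 0.40) at that r |
|---|---|---|---|
| 14 | 9 | 9 | 0.966 |
| 21 | 13 | 13 | 0.979 |
| 28 | 16 | 16 | 0.967 |
| 35 | 19 | 19 | 0.957 |
| 42 | 23 | 23 | 0.974 |
| 49 | 26 | 26 | 0.969 |
| 56 | 29 | 29 | 0.964 |
| 63 | 32 | 32 | 0.960 |

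All eight match. A Beta(0.8, 1.2) prior, centred on 40%, gives the same eight limits. The prior is therefore not identified, but the reference value of 40% is well supported.

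**Step 2: put 40% at two years on the 3-month scale.** With a constant hazard, the 3-month rate is 1 − (1 − 0.40)^(3/24) = 1 − 0.6^(1/8) = 0.062. Expected relapses among 14 patients are 14 × 0.062 = 0.87.

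**Step 3: chance of stopping.** The first look is P(X ≥ 9) for X ~ Binomial(14, p). The last column is the exact probability of crossing any of the eight limits. Checking after every patient gives the same result, because the limit is constant within a band.

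| Assumed 3-month rate p | First look | All eight looks |
|---|---|---|
| 5% | 3 × 10⁻⁹ | 3 × 10⁻⁹ |
| 6.2% (constant hazard) | 2 × 10⁻⁸ | 2 × 10⁻⁸ |
| 10% (a quarter of two-year relapses) | 1.3 × 10⁻⁶ | 1.3 × 10⁻⁶ |
| 20% (half) | 0.04% | 0.04% |
| 30% (three quarters) | 0.8% | 1.2% |
| 40% (all) | 5.8% | 14.2% |

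An even chance of stopping at the first look needs a 3-month relapse rate of about 60%.

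**Step 4: sensitivity to the clock.** Follow-up is counted in the study, and enrolment may be as late as about day +28, so the window may reach about four months after transplant. Then 1 − 0.6^(4/24) = 0.082, and P(X ≥ 9) = 2 × 10⁻⁷.

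**Step 5: what matching the time scale does.** The Step 1 rule, centred on a 3-month rate of 6.2%, 10%, 15% or 20%, puts the first limit at 3, 4, 5 or 6 of 14 instead of 9. At those same rates the chance of stopping at the first look is 5.2%, 4.4%, 4.7% and 4.4%. Re-centring thus brings the limit into the possible range. A rule that demands 95% certainty of being worse than historical will still rarely stop a regimen that merely equals historical.

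**Step 6: arithmetic in the same section.** 14 + 54 = 68, not 67. The last table column ends at 63. The first column as printed reads <14 patients and >9 relapses, where the text has 9 or more of 14.

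**The case against.** The strongest points on the other side are these.

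- **The derivation is inferred.** The plan states no prior, no cut-off and no derivation of the relapse row. That is true, but eight matches in eight under two priors leave little room for a 3-month adjustment.
- **The 3-month rate is assumed, and the documents' timing evidence is indirect.** The statement "Patients with increasing host chimerism sustained relapses between days 36 and 450 of their follow-up" concerns a selected subgroup in a cited series. The late relapses in Section 1.11 came after 24 months, so they lie outside the two-year rate and do not show what share of it falls in the first three months. Both criticisms stand, and neither source is used to set the rate. The conclusion rests on the whole range in Step 3, including the extreme at which every two-year relapse occurs by three months.
- **Stopping only when relapse is credibly worse than historical is a recognised conservative choice.** That is fair. It is a separate matter from the time-scale mismatch and would not by itself call for a change. The 14.2% figure also treats each table column as a look. If only the look at 14 patients is formal, 5.8% applies.
- **Other protections exist.** Section 7.1.3 lets the PI stop if treatment proves less effective than standard, and there are separate SAE and GVHD limits. Section 7.1.3 is discretionary and has no threshold, and the safety limits do not address efficacy.
- **Final inference is unharmed.** A futility rule that never triggers does not inflate type I error or bias the final relapse proportion. This is correct: the damage is to the interim decision.
- **The table symbols may have been lost in text extraction, and 54 may be a slip.** Both are possible. These are points to tidy and not part of the main finding.

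**Conclusion.** The concern holds. The relapse limits are calibrated to 40%, a figure the plan pairs with a two-year endpoint, and are applied to relapses within three months. Under an ineffective regimen the first look stops with probability 2 × 10⁻⁸ at a constant hazard and 0.04% if half of two-year relapses are early. Even if all of them are early, the figure is only 5.8% (14.2% over eight looks). The one outside assumption is the 3-month rate. No value up to the full 40% gives the rule a useful chance of stopping; at that extreme the description softens from essentially none to low. Because this is a decision threshold that cannot do its stated job, it should be corrected before the rule is relied on.

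**What to change.** Re-derive the relapse row on a time scale that matches the count, in one of two ways:

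1. Use the relapse dates in the sponsor's pilot data to estimate the 3-month rates that correspond to 40% and 25% at two years, and set the limits from those. The series is small, so show the limits over a range of rates.
2. Count all relapses to date in a time-to-event Bayesian or predictive-probability rule against the two-year target.

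For either rule, state the prior, the cut-off, the clock (transplant or enrolment) and which looks are binding. Print the probability of stopping at the 40% and 25% scenarios, as Section 8.7.2 does for SAEs. As Step 5 shows, re-centring alone leaves only about a 5% chance of stopping at the first look under the reference rate. The team should therefore decide openly whether the rule guards only against harm relative to historical or also asks whether 25% is still within reach.

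In the same edit, change 54 to 53, make the first table column agree with 9 or more of 14, and extend the table to 67. Say whether the end-of-study limit of 32 counts 3-month or two-year relapses.

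The cost is a short recalculation and a revised table, with no extra patients or data collection. A rule that can trigger carries a small loss of power, which the printed stopping probability at 25% will help to quantify.

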8.4 Sample size

- 8.4.1 The sample size is estimated using Bayesian sequential monitoring design with toxicity and response outcomes as multiple endpoints(45). It is assumed that the rate of relapse in pediatric acute leukemia post-transplant would be 40% (as shown in our pilot study), azacitidine +/- DLI would reduce the 2-year relapse rate by approximately 40% to a rate of 25%. A sample size of 67 evaluable patients is required to provide 80% power at a one-sided significance level of 0.05 to test the hypothesis based on the relapse rate of H0: relapse rate > 40% (historically-controlled) versus Ha: relapse rate < 25% (treatment-targeted). The study will enroll patients until accrual of 67 patients is achieved.
- 8.4.2 Enrollment of 67 patients will be attainable with enrollment at multiple centers. Investigators from All Children's Hospital, Lucille Packard Children's Hospital have written letters of support expecting to enroll 30-40 patients over 2 years.

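### Section 8.7.3 is internally inconsistent: 14 + 54 is 68, not 67; the first column of the stopping table disagrees with the text; and no toxicity limit is given beyond 63 patients

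*Combined protocol and SAP*

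**What the plan says.** Section 8.7.3 fixes the time of the early look: "Such early futility assessment will be done when the first 14 patients have completed the 3-month follow-up in the study". It gives the rule in words: "If there are 9 or more relapses out of 14 patients during the futility assessment, enrollment will be stopped due to futility". If the rule is not met, "Otherwise an additional 54 patients will be accrued for a total of 67 patients in the study". It adds an end-of-study criterion of 32 or more relapses.

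The table in the same section restates the limits by number of patients on study. Its header begins "Patients on Study <14 15-21 22-28" and its last column is 57-63. The relapse row begins "Number of patients with relapse in 3 months >9 ≥13" and ends at ≥32. The toxicity row begins with >8 and ends at ≥26.

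Section 8.4.1 gives the total as 67 evaluable patients and adds: "The study will enroll patients until accrual of 67 patients is achieved". Sections 8.5.1 and 8.7.1 also give 67. Section 7.1.2 makes the rules of 8.7.3 a ground for terminating the study.

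**The concern.** Text and table describe the same monitoring scheme, and a committee will apply them literally. Three things do not fit.

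1. The first-stage size and the additional accrual do not add to the stated total.
2. On the symbols as supplied, the table leaves out the exact sample size at which the look takes place, and its relapse limit is one higher than the text's. With 9 relapses in 14, one part of the section closes enrolment and the other does not. The toxicity cell has the same symbol, and no sentence says whether 8 or 9 events triggers it.
3. The table stops four patients short of full accrual. For relapse the end-of-study sentence fills the gap; for toxicity nothing does.

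Because Section 7.1.2 ties termination to these rules, they should not need interpretation when they are applied.

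**Working it through.** **The plan's own total.** Inputs from Section 8.4.1: relapse 40% (null) against 25% (target), one-sided 0.05, power 80%.

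- Normal approximation with null variance: n = (1.645 + 0.842)² × 0.40 × 0.60 / (0.40 − 0.25)² = 65.9, so 66.
- Null and alternative variances: 60.9, so 61; with continuity correction 67.4, so 68.
- Exact binomial at n = 67: reject at 19 or fewer relapses, one-sided error 3.2%, power 78.4%.

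The stated 67 lies within the spread of the usual formulas and is not in question.

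**Accrual sum.** 14 + 54 = 68. 67 − 14 = 53. Four other statements of the total (the opening summary, 8.4.1, 8.5.1 and 8.7.1) and the sentence itself say 67, so 54 is the likely slip.

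**First look, text against table as supplied.**

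| Item | Text of 8.7.3 | Table of 8.7.3 |
|---|---|---|
| Patients at the look | 14 | <14, then 15-21 |
| Relapse limit | 9 or more | >9, i.e. 10 or more |
| Toxicity limit | not stated | >8, i.e. 9 or more |

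The separate SAE table in 8.7.2 gives ≥6 for 14-17 patients, so it cannot show whether 8 or 9 was meant here.

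**What one relapse changes.** Stopping probability = P(X ≥ r), X binomial with n = 14 and relapse probability p within 3 months. The documents give no 3-month rate. The 40% and 25% are their 2-year rates; 10% and 20% are assumptions to show the range.

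| p | P(X ≥ 9) | P(X ≥ 10) |
|---|---|---|
| 40% | 5.8% | 1.8% |
| 25% | 0.22% | 0.03% |
| 20% (assumed) | 0.038% | 0.005% |
| 10% (assumed) | 0.0001% | <0.0001% |

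**End of the table.** The last column closes at 63; 67 − 63 = 4 patients (4/67 = 6%). For relapse, the end-of-study limit of 32 equals the limit in the 57-63 column. For toxicity there is no such sentence, and the 8.7.2 table ends at 27 patients.

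**The case against.** The strongest objection concerns the first column. All three odd symbols sit there. If each has lost a bar in PDF reading, they become ≤14, ≥8 and ≥9. That matches the text, joins exactly to 15-21, and fits column ends at multiples of 7. One cause would remove the missing 14, the relapse conflict and the doubt over the toxicity cell. This is plausible and cannot be excluded from the supplied text. It is not established either: the sign ≥ survives in the other 14 limit cells of this table and in all six of the 8.7.2 table. If it is right, the second item falls and the first and third stand.

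Two further objections hold and limit the point.

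- A reader might infer that the trial would over-enrol by one patient. Section 8.4.1 ends accrual at 67, so the wrong figure is an intermediate count.
- A reader might infer that patients 64 to 67 have no stopping limit at all. That is so only for the toxicity table. Relapse has the end-of-study rule, and DSMC review of serious events and the GVHD suspension rule for patients receiving DLI continue to apply.

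A reader might also take 5.8% against 1.8% as a threefold change of practical weight. Those figures apply a 2-year rate to a row headed "Number of patients with relapse in 3 months". At lower rates the ratio is larger, but both probabilities are close to zero.

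**Conclusion.** The section needs correction, at modest weight.

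- **Accrual sum:** certain, and independent of how the PDF was read. It is off by one patient in an intermediate figure, with no effect on the total of 67.
- **First column:** a real conflict on the text as supplied, conditional on the symbols being as printed. It then amounts to one relapse at one look and an unresolved toxicity cell. The chance that the one-relapse difference decides the look is 5.8% − 1.8%, about 4 percentage points, if 40% relapsed within 3 months, and under 0.04 points at an assumed 10-20%.
- **End of the table:** certain for toxicity only, covering the last four patients (6%).

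None of this challenges the sample size. The probabilities assume independent patients with a common relapse probability.

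**What to change.** 1. In the 8.7.3 text, change 54 to 53.
2. Check the first-column symbols against the source document. If they read ≤14, ≥8 and ≥9, nothing more is needed there. If they are as printed, set the column to ≤14 and the relapse cell to ≥9 to agree with the text, and confirm the toxicity limit from the design output.
3. Add a final column covering 64-67 patients, with limits computed from the same sequential design. Stretching 57-63 to 67 with ≥26 and ≥32 unchanged would apply limits to a larger denominator without derivation.

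The cost is one number, one table and one run of the existing design calculation. Sample size, endpoints and timing of the look do not change.

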We plan to enroll 67 children with hematologic malignancies (including acute myeloid leukemia, acute lymphoblastic leukemia, juvenile myelomonocytic leukemia, and myelodysplastic syndrome) at the time of HSCT at three institutions (including UCSF, All Children's Hospital, St. Petersburg, FL, and Lucile Packard Children's Hospital, Palo Alto, CA). Patients will be enrolled on the study by day +28, prior to withdrawal of immunosuppression or administration of donor lymphocyte infusion (DLI). They will have donor chimerism and minimal residual disease (MRD) testing from the peripheral blood (PB) and bone marrow (BM) on day $+28 \pm 7$ (as per standard of care). Based on risk assessment, patients will receive one cycle of low-dose azacitidine ($40\text{mg}/\text{m}^2$ IV/SC daily $\times 4$ days) alone as immunosuppression is tapered. After tapering immunosuppression, chimerism will be repeated and patients will receive up to 6 additional cycles of low-dose azacitidine. For patients who meet at high risk for relapse, azacitidine will be combined with escalating doses of DLI for a maximum of 7 cycles in total. Risk and safety assessments, including routine laboratory parameters, donor chimerism, minimal residual disease, and GHVD activity will be assessed following each cycle.

The primary outcome measures will be indicators of relapse risk and safety / toxicity. Patients will be followed for relapse as well as incidence of severe drug toxicities and acute and chronic GVHD until 2 years post-transplant. The study will be considered successful if the rate of relapse at 2 years is $<25\%$, and the incidence of Grade IV GVHD and severe drug toxicity are $<20\%$. Correlative studies will include the effect of azacitidine on T cell immune reconstitution, as well as prospective minimal residual disease estimation by gene expression / mutation panels in patients with AML.

Study Schema

Standard Risk:

- Active Grade I GVHD, OR
- Any history of >Grade II GVHD, OR
- Full Donor Chimerism AND Pre-HSCT MRD-neg AND Post-HSCT MRD-neg

High Risk:

- No GVHD or resolved Grade I GVHD, AND
- Mixed chimerism OR Pre-Tx MRD(+) OR Post-Tx MRD(+)

[figure not shown]

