8.6 Statistical Analysis

- 8.6.1 Patient demographics and baseline characteristics including age, sex, race, ethnicity and medical conditions will be summarized using descriptive statistics. For quantitative parameters, descriptive statistics will include the mean, standard deviation, minimum, median and maximum. For qualitative parameters, descriptive statistics will include the frequency and proportions.
- 8.6.2 The primary endpoint parameters: (1) relapse rate and (2) incidence of Grade III-IV aGVHD, severe cGVHD, and Grade IV toxicities, will be estimated using proportions with 95% CI.
- 8.6.3 The chimerism parameters (CD3+, CD14/15+, CD19+, CD33+, CD34+) and incidence of acute and chronic GVHD will also be analyzed using descriptive statistics including means, standard deviation and 95% CI.

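### Section 8.4.1 sizes the trial for a one-sided 0.05 test of 40% against 25% relapse, but no final relapse criterion in the protocol is that test

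*Combined protocol and SAP*

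**What the plan says.** Four places bear on the final relapse conclusion.

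- **Section 8.4.1.** The sample size is attributed to a Bayesian sequential monitoring design with toxicity and response outcomes. The justification is then frequentist: "A sample size of 67 evaluable patients is required to provide 80% power at a one-sided significance level of 0.05", for "H0: relapse rate > 40% (historically-controlled) versus Ha: relapse rate < 25% (treatment-targeted". No critical count, test, prior or posterior cut-off is given.
- **Section 8.7.3.** "By the end of the study, if there are 32 or more relapses observed, further investigation will not proceed". The accompanying table has a row headed "Number of patients with relapse in 3 months", whose last limit, for 57 to 63 patients, is also 32. The same section says, after the look at 14 patients, "Otherwise an additional 54 patients will be accrued for a total of 67 patients in the study".
- **Synopsis (opening summary).** "The study will be considered successful if the rate of relapse at 2 years is" below 25%, together with limits on severe GVHD and drug toxicity. It does not say whether the 25% is an observed rate or a true rate.
- **Section 8.6.2.** The primary endpoint parameters "will be estimated using proportions with 95% CI". No interval method, reference value or decision rule is stated.

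**The concern.** A single-arm trial against a historical rate controls its error rates only if the final cut-off is fixed in advance. Here the test that justifies the sample size has no printed cut-off, and the final statements that are printed lead to different rules. A result in the high teens of relapses could be called positive or negative depending on the section consulted and on a choice of method left open until the data are known. The 32-relapse sentence adds to this: it is worded as the end-of-study rule for a 2-year endpoint, but its number matches a limit in a 3-month monitoring row.

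**Working it through.** **Inputs.** N = 67, one-sided alpha 0.05, power 80%, p0 = 0.40, p1 = 0.25 (8.4.1); no-go limit 32 (8.7.3); below 25% (synopsis); 95% CI (8.6.2). The documents name no test, so exact binomial tails are used, with all 67 patients assumed to have known 2-year status.

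**1. The plan's own figure.** One-sample normal approximation:

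n = [(1.645·√(0.40·0.60) + 0.842·√(0.25·0.75)) / 0.15]² = 60.9.

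With continuity correction: (60.9/4)·[1 + √(1 + 2/(60.9·0.15))]² = 67.4. The exact test at N = 67 has power 0.784. So 67 is consistent with a one-sided one-sample binomial test.

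**2. The test implied by 8.4.1.** Find the largest c with P(X ≤ c | 67, 0.40) ≤ 0.05:

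- c = 19: alpha 0.0324, power P(X ≤ 19 | 0.25) = 0.784.
- c = 20: alpha 0.0563, above 0.05 (power 0.855).

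The exact rule is 19 or fewer. An uncorrected normal test would also reject at 20: z = (0.2985 − 0.40)/√(0.24/67) = −1.70, p = 0.045, although the exact alpha is then 0.056.

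**3. The 32-relapse limit.** 32/67 = 47.8%. P(X ≥ 32 | 0.40) = 0.121; P(X ≥ 32 | 0.25) = 0.00005.

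**4. Synopsis 25% read as an observed rate.** 16/67 = 23.9% and 17/67 = 25.4%, so the rule is 16 or fewer.

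**5. The 8.6.2 interval, if compared with 40%.** Two-sided 95% upper limits:

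| Relapses | Exact | Wilson | Wald |
|---|---|---|---|
| 18 | 39.1% | 38.5% | 37.5% |
| 19 | 40.7% | 40.1% | 39.2% |
| 20 | 42.3% | 41.7% | 40.8% |

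Exact and Wilson intervals exclude 40% at 18 or fewer, Wald at 19 or fewer.

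**6. The candidate success rules side by side (N = 67).**

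| Rule | Source | Alpha at 40% | Power at 25% |
|---|---|---|---|
| ≤16 | Synopsis, if observed rate | 0.004 | 0.481 |
| ≤18 | 8.6.2, exact or Wilson CI against 40% | 0.018 | 0.695 |
| ≤19 | 8.4.1, exact test; also Wald CI against 40% | 0.032 | 0.784 |
| ≤20 | 8.4.1, uncorrected normal test | 0.056 | 0.855 |

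**7. How often the choice matters.** P(17 to 19 relapses | 0.25) = 0.784 − 0.481 = 0.302. In that range the exact test rejects 40%, but the synopsis rule, if it is an observed bar, fails.

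**8. Dependence on N.** In 8.7.3, 14 + 54 = 68, not 67. At N = 68 the exact cut-off is 20 or fewer (alpha 0.047, power 0.837).

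**The case against.** Much of the opposing case stands.

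- **The 32 limit is a stopping rule, not an efficacy test.** It sits under a futility heading, and its consequence is a no-go. A limit for results worse than history may properly lie above 40%. A reader might infer that 31 or fewer means success, which would give a type I error of 1 − 0.121 = 0.879. No section says so.
- **The synopsis may only restate the target.** Section 8.4.1 labels the 25% under Ha as treatment-targeted. On that reading the 48% power and the 30% chance of conflict both disappear. A reader might infer that the trial has only 48% power; the documents do not establish that. What remains is that no count goes with the success statement.
- **Section 8.6.2 is an estimation statement.** The mismatch at 19 relapses arises with exact and Wilson intervals but not with Wald, and no method is named.
- **The exact test is an assumption.** Section 8.4.1 names a Bayesian design, which could carry its own cut-off. None is printed, so this does not supply the missing rule.
- **The sample size is not wrong.** A reader might infer an error in the 67, but it reproduces.

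**Conclusion.** The point holds as a gap in the decision rule: the one-sided 0.05, 80% power test that justifies N = 67 is not carried into any final criterion. The one printed final count (32) answers a different question. The one printed success statement (below 25%) either has no count or, as an observed rate, has 48% power. The interval in 8.6.2 decides nothing as written. Depending on reading and method, the success cut-off could be 16, 18, 19 or 20 relapses.

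The cut-off of 19 with 78% power rests on an exact one-sided binomial test and on 67 evaluable patients with known 2-year status. Section 8 does not say how death without relapse or loss to follow-up enters the proportion. The plan should be corrected on this point before the final analysis. The enrolment target need not change.

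**What to change.** 1. State one final 2-year relapse success rule, identical in the synopsis, 8.4.1 and 8.7.3. Name the test and reconcile it with the Bayesian design sentence, either by giving that design's prior and cut-off or by limiting it to monitoring.
2. If the exact one-sided binomial test is chosen: at 67 evaluable patients, conclude that relapse is below 40% with 19 or fewer relapses (alpha 0.032), and restate power as 78%. Give the cut-off for other evaluable numbers, for example 20 or fewer at 68 (alpha 0.047, power 84%).
3. In 8.6.2, name the interval method and add the matching exact one-sided 95% upper bound (38.8% at 19 relapses, 40.4% at 20), so that interval and test agree.
4. Say whether the synopsis 25% is the targeted true rate or an observed bar. If an observed bar, print its 48% power.
5. Keep the 32 limit, but label it a no-go limit and not the efficacy test. State whether it counts 3-month or 2-year relapses. Make clear which limit covers patients 64 to 67, since the table ends at 63 and the end-of-study sentence is the only relapse limit that could reach them.
6. In 8.7.3, correct 54 to 53, so that 14 + 53 = 67.

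The cost is wording only, with no extra patients. The downside is that stated power falls from 80% to 78% under the exact test.
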